### **6.5. Storage Conditions**

Test articles will be maintained at ambient temperatures at the clinical site. Test articles must be kept under secure conditions.

### **6.6. Collection and Storage of Samples**

When possible, any test article associated with an Adverse Events and/or a Product Quality Complaint must be retained pending directions from the sponsor for potential return back to JJV.

### **6.7. Accountability of Test Articles**

JJV will provide the Investigator with sufficient quantities of study articles and supplies to complete the investigation. The Investigator is asked to retain all shipment documentation for the test article accountability records.

Test article must be kept in a locked storage room, accessible only to those assigned by the Investigator for dispensing. The Investigator may delegate this activity to authorized study site personnel listed on the Site Delegation Log. All test articles must be accounted. This includes:

1. What was dispensed for the subject
2. What was returned to the Investigator unused
3. The number and reason for unplanned replacements

The Investigator will collect all unused test articles from the subjects at the end of the subject's participation. Subject returned unused test articles must be separated from the clinical study inventory of un-dispensed test articles, and must be labeled with the subject number and date of return. Following final reconciliation of test articles by the monitor, the Investigator or monitor will return all unused test articles to JJV.

If there is a discrepancy between the shipment documents and the contents, contact the study monitor immediately.

Reference [REDACTED] Site Instructions for Test Article Receipt and Test Article Accountability for additional information.

## 7. STUDY EVALUATIONS

### 7.1. Time and Event Schedule

Table 3: Time and Events

Visit Information	Visit 0 Optional pre-screen	Visit 1 Baseline, dispense drop #1	Visit 2 Follow-up drop #1	Washout	Visit 3 Dispense drop #2	Visit 4 Follow-up drop #2
Time Point			7-9 days after V1	7-9 days	7-9 days after V2	7-9 days after V3
Estimated Visit Duration		3 hours	1.5 hours		3 hours	1.5 hours
Phone/ electronic consent	X					
Study Informed Consent		X				
Inclusion/Exclusion Screening Criteria		X				
Demographics		X				
Medical History & medication review		X	X		X	X
Habitual Artificial Tear usage		X				
DEQ-5	X	X	X		X	X
OSDI		X	X		X	X
Biomicroscopy		X	X		X	X
Eligibility		X				
Randomization		X				
LipiView II®		X	X		X	X
Pre-drop VAS comfort		X			X	
Drop #1 instillation		X				
Drop #2 instillation					X	
LipiView II® follow up (5 minutes, 30 minutes, 60 minutes, 120 minutes)		X			X	
Post-drop VAS comfort/questionnaires (5 minutes, 30 minutes, 60 minutes, 120 minutes)		X			X	
NITBUT		X	X		X	X
Ocular Symptoms		X	X		X	X
Drop Dispensing & Instruction		X			X	
Drop Usage questions		X	X		X	X
Follow-up VAS comfort/questionnaires			X			X
Exit Slit-lamp			X		X	X
Adverse Event Review			X		X	X
Final Evaluation						X

## 7.2. Detailed Study Procedures

### VISIT 0

Optional pre-screen that may occur

Visit 0: Pre-Screening			
Step	Procedure	Details	
0.1	Phone/electronic Consent	Obtain Consent from the subject utilizing an EC-approved consent	
0.2	Pre-screen DEQ-5	
The subject will respond to the DEQ-5.
 
 
• If the DEQ-5 sum score is greater than 6 then schedule Visit 1 for screening
 
• If DEQ-5 sum score is less or equal than 6, subject is not deemed eligible for further screening.
 
	

### VISIT 1

The subjects must present to Visit 1 wearing their spectacles (if applicable) having not used any artificial tears that day. Subjects will be asked to bring their habitual artificial tears with them to the visit (if applicable).

Visit 1: Screening			
Step	Procedure	Details	
1.1	Statement of Informed Consent	
Each subject must read, understand, and sign the Statement of Informed Consent and Privacy Statement before being enrolled into the study. The Principal Investigator or their designee conducting the informed consent discussion must also sign the consent form.
 
Note: The subject must be provided a signed copy of this document.
	
1.2	Demographics	Record the subject's date of birth, gender, race and ethnicity.	
1.3	Medical History and Concomitant Medications	Questions regarding the subjects' medical history and concomitant medications.	
1.4	Artificial Tear Use	The subject will be asked about their artificial tear use.	
1.5	DEQ-5 Questionnaires	The subject will respond to the DEQ-5 questionnaire.	Appendix A
1.6	Eligibility after Screening	All responses to Screening Inclusion Criteria questions must be answered "yes" and all responses to Exclusion Criteria must	

Visit 1: Screening			
Step	Procedure	Details	
		be answered “no” for the subject to be considered eligible.	

Visit 1: Baseline			
Step	Procedure	Details	
1.7	OSDI Questionnaire	The subject will respond to the OSDI questionnaire.	Appendix A
1.8	VAS Questionnaire	The subject will respond to the VAS comfort questionnaire	Appendix A
1.9	Entrance Visual Acuity	Record the distance high contrast visual acuity to the nearest letter (OD, OS, and OU) with their habitual spectacle correction in place (or unaided if applicable).	EuroLens Research SOP
1.10	Tear film lipid layer thickness	Record the tear film lipid layer thickness, OD & OS	Measure per LipiView II® II manufacturer instruction (Appendix D)
1.11	Habitual tear film stability (Medmont)	Record the tear film stability (NITBUT), OD & OS	NITBUT Medmont Work Aid (Appendix E)
1.12	Slit Lamp Biomicroscopy	
The FDA slit lamp classification scale will be used to grade the findings and determine eligibility.
 
If there are any Grade 2 or higher other slit-lamp findings, the subject is ineligible to continue at this time, but may return up to one additional time to determine eligibility. If discontinued a final examination must be completed.
 
If there are no slit lamp findings, and the clearance of the fluorescein needs to be expedited, preservative-free rewetting drops or saline may be instilled.
	
1.13	Expanded Sodium Fluorescein Corneal Staining	Corneal Staining Assessment (FDA grading scale) will be assessed using a more detailed scale for internal purposes only.	

Visit 1: Baseline			
Step	Procedure	Details	
1.14	Eligibility after Baseline	All responses to Inclusion Criteria questions must be answered “yes” and all responses to Exclusion Criteria questions must be answered “no” for the subject to be considered eligible.	

Visit 1: Dispense Drop #1			
Step	Procedure	Details	
1.15	Randomization	Subjects will be randomized to an artificial tear order.	
1.16	Drop instillation	The subject will instill 1 drop in both eyes (or drops can be instilled by the investigator should the subject require drop installation training).  The investigator should observe the subject’s technique for drop instillation and recommend new techniques to improve subject safety, if necessary.	
1.17	Ocular Symptoms	Subjects will respond to a verbal open-ended symptoms questionnaire.	
1.18	Drop Settling	Allow the drop to settle for 5 minutes.	
1.19	Tear film lipid layer thickness-5 minutes	Record the tear film lipid layer thickness, OD & OS	Measure per LipiView II® II manufacturer instruction (Appendix D)
1.20	VAS Questionnaire	The subject will respond to the VAS comfort questionnaire	
1.21	Tear film lipid layer thickness- 30 minutes	Record the tear film lipid layer thickness, OD & OS	Measure per LipiView II® II manufacturer instruction (Appendix D)
1.22	VAS Questionnaire	The subject will respond to the VAS comfort questionnaire	
1.23	Tear film lipid layer thickness- 60 minutes	Record the tear film lipid layer thickness, OD & OS	Measure per LipiView II® II manufacturer instruction (Appendix D)

Visit 1: Dispense Drop #1			
Step	Procedure	Details	
1.24	VAS Questionnaire	The subject will respond to the VAS comfort questionnaire	
1.25	Tear film lipid layer thickness- 120 minutes	Record the tear film lipid layer thickness, OD & OS	Measure per LipiView II® II manufacturer instruction (Appendix D)
1.26	VAS Questionnaire	The subject will respond to the VAS comfort questionnaire	
1.27	Exit Visual Acuity	Record the distance high contrast visual acuity to the nearest letter (OD, OS, and OU) with their habitual spectacle correction in place (or unaided if applicable).	Eurolens Research SOP
1.28	Continuance	For the subject to continue in the study, they must meet both of the following criteria: 
 
• Visual acuity is 20/30 (0.18logMAR) or better OD and OS
 
• Subject willing to use the drop at least 3x a day OU for 7-9 days.
 
	
1.29	Instillation of drops training	Instruct and teach instillation of drops.	
1.30	Dispense	The artificial tears will be dispensed for a 7-9 day wearing period 
 
• Dispense enough artificial tears to last the whole week.
 
• A patient instruction guide will be provided.
 
• Subjects will be scheduled for Visit 2 in approximately 7-9 days.
 
	

## VISIT 2

The subjects must present to visit 2 wearing their habitual spectacles (if applicable) having used the study drop in both eyes at least 2 times that day.

Visit 2: Follow-up on drop #1			
Step	Procedure	Details	
2.1.	Adverse Events and Concomitant Medications Review	Review any changes to the subject's medical history or concomitant medications from the previous study visit. Record any changes, and any adverse events.	

Visit 2: Follow-up on drop #1			
Step	Procedure	Details	
2.2.	Artificial Tear Use	The subject will be asked about their artificial tear use.	
2.3.	Collection of Study drops	The site will collect and discard the bottle of study eye drops.	
2.4.	Subject Reported Ocular Symptoms	Subjects will respond to a verbal open-ended symptoms questionnaire.	
2.5.	DEQ-5 Questionnaires	The subject will respond to the DEQ-5 Questionnaires.	Appendix A
2.6.	OSDI questionnaire	The subject will respond to the OSDI questionnaire.	Appendix A
2.7.	VAS Questionnaire	The subject will respond to the VAS comfort questionnaire	
2.8.	Visual Acuity	Record the distance high contrast visual acuity to the nearest letter (OD, OS, and OU) with their habitual spectacle correction in place (or unaided if applicable).	Eurolens Research SOP
2.9.	Tear film lipid layer thickness	Record the tear film lipid layer thickness, OD & OS	Measure per LipiView II® II manufacturer instruction (Appendix D)
2.10.	Habitual tear film stability (Medmont)	Record the tear film stability (NITBUT), OD & OS	NITBUT Medmont Work Aid (Appendix E)
2.11.	Slit Lamp Biomicroscopy	The FDA slit lamp classification scale will be used to grade the findings.  (All ocular AE's must be followed to resolution)  If the clearance of the fluorescein needs to be expedited, preservative-free rewetting drops or saline may be instilled.	
2.12.	Expanded Sodium Fluorescein Corneal Staining	Corneal Staining Assessment (1.0 scale units) will be assessed using a more detailed scale for internal purposes only.	
2.13.	Exit Visual Acuity	Record the distance high contrast visual acuity to the nearest letter (OD, OS, and OU) with their habitual spectacle correction in place (or unaided if applicable).	Eurolens Research SOP

Visit 2: Follow-up on drop #1			
Step	Procedure	Details	
2.14.	Washout instructions	Instruct subject they may use any habitual drops during their washout of 7-9 days	

### VISIT 3

The subjects must present to visit 3 wearing their habitual spectacles (if applicable) having not used any artificial tears that day.

Visit 3: Dispense Drop #2			
Step	Procedure	Details	
3.1.	Adverse Events and Concomitant Medications Review	Review any changes to the subject's medical history or concomitant medications from the previous study visit. Record any changes, and any adverse events.	
3.2.	Artificial Tear Use	The subject will be asked about their artificial tear use.	
3.3.	Subject Reported Ocular Symptoms	Subjects will respond to a verbal open-ended symptoms questionnaire.	
3.4.	DEQ-5 Questionnaires	The subject will respond to the DEQ-5 Questionnaires.	
3.5.	OSDI questionnaire	The subject will respond to the OSDI questionnaire.	
3.6.	VAS Questionnaire	The subject will respond to the VAS comfort questionnaire	
3.7.	Entrance visual acuity	Record the distance high contrast visual acuity to the nearest letter (OD, OS, and OU) with their habitual spectacle correction in place (or unaided if applicable).	Eurolens Research SOP
3.8.	Tear film lipid layer thickness	Record the tear film lipid layer thickness, OD & OS	Measure per LipiView II® II manufacturer instruction (Appendix D)
3.9.	Habitual tear film stability (Medmont)	Record the tear film stability (NITBUT), OD & OS	NITBUT Medmont Work Aid (Appendix E)

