3.24.	Continuance	For the subject to continue in the study, they must meet both of the following criteria: 
 
• Visual acuity is 20/30 or better OD and OS
 
• Subject willing to use the drop at least 3x a day for 7-9 days.
 
	
3.25.	Dispense	The artificial tears will be dispensed for a 7-9 day wearing period 
 
• Dispense enough artificial tears to last the whole week.
 
• A patient instruction guide will be provided.
 
 Subjects will be scheduled for Visit 4 in approximately 7-9 days.	Dispense

#### VISIT 4

The subjects must present to visit 4 wearing their habitual spectacles (if applicable) having used the study drop in both eyes at least 2 times that day.

Visit 4: Follow-up of Drop #2			
Step	Procedure	Details	
4.1.	Adverse Events and Concomitant Medications Review	Review any changes to the subject's medical history or concomitant medications from the previous study visit. Record any changes, and any adverse events.	
4.2.	Artificial Tear Use	The subject will be asked about their artificial tear use.	
4.3.	Collection of Study drops	The site will collect and discard the bottle of study eye drops.	

Visit 4: Follow-up of Drop #2			
Step	Procedure	Details	
4.4.	Subject Reported Ocular Symptoms	Subjects will respond to a verbal open-ended symptoms questionnaire.	██████████
4.5.	Modified DEQ-5 Questionnaires	The subject will respond to the modified DEQ-5 Questionnaires.	██████████ Appendix A
4.6.	OSDI Questionnaire	The subject will respond to the OSDI questionnaire.	██████████ Appendix A
4.7.	VAS Questionnaire	The subject will respond to the VAS comfort questionnaire	██████████
4.8.	Visual Acuity	Record the distance high contrast visual acuity to the nearest letter (OD, OS, and OU) with their habitual spectacle correction in place (or unaided if applicable).	Eurolens Research SOP ██████████
4.9.	Tear film lipid layer thickness	Record the tear film lipid layer thickness, OD & OS	Measure per LipiView II® II manufacturer instruction (Appendix D)
4.10.	Habitual tear film stability (Medmont)	Record the tear film stability (NITBUT), OD & OS	NITBUT Medmont Work Aid (Appendix E)
4.11.	Slit Lamp Biomicroscopy	The FDA slit lamp classification scale will be used to grade the findings.  (All ocular AE's must be followed to resolution)  If the clearance of the fluorescein needs to be expedited, preservative-free rewetting drops or saline may be instilled.	██████████

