### 2.3 *Precautions*

The following patient conditions may affect the interferometry assessment of a patient's tear film using LipiView II:

- **Use of ophthalmic drops such as artificial tear lubricants, ointments, and medications.** Advise patients not to instill oil-based ophthalmic drops (e.g., Soothe®, Restasis®, Systane Balance®) for at least 12 hours prior to device use and not to instill ointments for at least 24 hours prior to device use. Wait at least 4 hours after instillation of all other ophthalmic drops prior to device use.
- **Soft or rigid contact lens wear.** Advise patients to remove contact lenses at least 4 hours prior to device use.
- **Use of oil-based facial cosmetics around the eye.**
- **Eye rubbing.**
- **Recent swimming in a chlorinated pool.** Advise patients not to swim for at least 12 hours prior to device use.
- **Any ocular surface condition** that affects the stability of the tear film. These conditions include disease, dystrophy, trauma, scarring, surgery, or abnormality.

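### Same-day study drops are required before the Visit 2 and Visit 4 LipiView readings, but the cited device instructions ask for 12 or 4 drop-free hours, so the one-week lipid readings may reflect residual product

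*Combined protocol and SAP*

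**What the plan says.** **Preparation for Visits 2 and 4 (Section 7.2).** Subjects come to Visit 2 "having used the study drop in both eyes at least 2 times that day". Visit 4 has the same rule: "The subjects must present to visit 4 wearing their habitual spectacles (if applicable) having used the study drop in both eyes at least 2 times" on the day. No interval is set between the last drop and the lipid reading.

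**The measurement (steps 2.9 and 4.9).** Lipid layer thickness is recorded in each eye, with the direction "Measure per LipiView II® II manufacturer instruction (Appendix D").

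**The device instructions (Appendix D, 2.3 Precautions).** The list opens with "The following patient conditions may affect the interferometry assessment of a patient's tear film using LipiView II", and its first item is the use of ophthalmic drops. For one class of drop: "Advise patients not to instill oil-based ophthalmic drops" "for at least 12 hours prior to device use and not to instill ointments for at least 24 hours prior to device use". Systane Balance is one of three products named there as examples. For the rest: "Wait at least 4 hours after instillation of all other ophthalmic drops prior to device use".

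**The products (Sections 1.1 and 6.1).** The Control is Systane BALANCE, whose ingredients include mineral oil. The Test is a liposome drop that Appendix D does not name.

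**Visits 1 and 3.** Subjects attend "having not used any artificial tears that day", and a pre-drop lipid reading is taken.

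**Role of the reading.** Section 2.2 lists LipiView only at 5, 30, 60 and 120 minutes after instillation. Section 4.1 and Table 3 also schedule it at Visits 2 and 4. Section 14.7 makes LipiView analysis exploratory and leaves it to the responsible clinician.

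**The concern.** The protocol tells the site to follow Appendix D and also to prepare subjects in a way that Appendix D advises against. Nothing waives the precaution or acknowledges the departure.

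Both products are lipid-type drops and the instrument measures lipid thickness, so any product left on the eye bears directly on what is measured. The two drops may also fall under different intervals in the device's own instructions. A one-week Test-Control contrast in lipid thickness could then combine two things that the design cannot separate: drop still on the eye, and any change in the subject's own tear film after a week of use.

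The crossover does not remove this. Residual product belongs to the drop used in that period, so it stays with treatment in both sequences. The time since the last drop is also left to the subject. Section 1.2 sets no upper limit on daily drops, and the study bottle is collected at steps 2.3 and 4.3, before the reading.

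**Working it through.** The plan states no figure to reproduce. The check is whether the two rules can be met together.

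**Inputs**
- At least two uses of the study drop on the visit day (Section 7.2, Visits 2 and 4).
- Drop-free interval of 12 hours for oil-based drops and 4 hours for others (Appendix D, 2.3).
- Estimated length of Visits 2 and 4: 1.5 hours (Table 3).
- Clock time of the reading: not given, so a range is assumed.

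**Formula.** Latest permissible last drop = time of LipiView reading minus the drop-free interval.

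| LipiView at (assumed) | Last drop by, 12 h | Last drop by, 4 h |
|---|---|---|
| 09:00 | 21:00 the day before | 05:00 |
| 12:00 | 00:00 | 08:00 |
| 16:00 | 04:00 | 12:00 |
| 18:00 | 06:00 | 14:00 |

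**Control period.** The product is named in Appendix D, so 12 hours applies. Up to a noon reading, two same-day uses are impossible. At 16:00 both uses must be over by 04:00, and at 18:00 by 06:00. Both rules cannot realistically be met.

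**Test period.** If the liposome drop counts as oil-based, the same result follows. If it does not, 4 hours applies: a 16:00 reading is compatible with two uses by 12:00, but a 09:00 reading needs both by 05:00. Compliance is possible in the afternoon, but nothing requires it. A 1.5-hour visit cannot supply a 4-hour wait.

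**Comparison with the timed readings.** The 5 to 120 minute readings at Visits 1 and 3 also fall inside both intervals, but they are defined as post-drop and carry a fixed time. The Visit 2 and 4 reading has neither a post-drop label nor a time. The NITBUT step that follows it (2.10 and 4.10) is titled as a habitual tear film measure.

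**Visits 1 and 3 (secondary).** Suppose a habitual oil-based drop at 23:00 and a reading at 09:00 (both assumed): 1 h + 9 h = 10 h. This satisfies the protocol's same-day rule and falls 2 hours short of 12. It does satisfy the 4-hour interval for other drops.

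**The case against.** The best defence is that the Appendix D cross-reference points to the capture procedure and not to the precautions. The same direction is attached to the 5, 30, 60 and 120 minute readings, where neither interval could apply. The contrast between no drops on the day at Visits 1 and 3 and at least two at Visits 2 and 4 also suggests that an on-treatment reading was wanted. This is a fair reading, and it may be what was meant. But the protocol does not say so, and an on-drop reading without an elapsed time is hard to interpret. The defence changes the problem from a conflict to an undeclared departure with an undefined measure; the same clarification is needed.

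Time of last use may already be collected. Artificial tear use is asked at every visit and Table 3 lists drop usage questions, but their content is not visible in the public copy. That stands, so the request for a time field is conditional.

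Four stronger readings might be inferred, and the documents do not support them:
- *That the readings certainly contain residual product.* Appendix D says only that drops may affect the assessment.
- *That Visits 1 and 3 contradict Appendix D.* A subject can meet both rules there. The wording is merely less strict for a user of an oil-based habitual drop. Subjects may return to habitual products before Visit 3 and sequence is randomised, so added noise in the baseline is the supportable claim, not bias between products.
- *That a planned endpoint comparison is compromised.* No Visit 2 versus Visit 4 lipid comparison is specified.
- *That publication of these readings is planned.* Section 21 says only that the data could be used in scientific materials.

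**Conclusion.** The point holds. The Visit 2 and 4 preparation rule and the device instructions cited for the same visits are inconsistent, and no text resolves this. For the Control the inconsistency is close to unavoidable. For the Test it depends on whether the drop counts as oil-based and on the hour of the visit.

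The one-week lipid readings may therefore reflect residual product, to a degree that differs by product and by an uncontrolled time since the last drop. They cannot be read as one-week lipid layer status. Up to 50 to 60 subjects (the completion and randomisation targets) would contribute such readings in each treatment period. The effect in nanometres, and its direction between products, cannot be derived from the documents.

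The consequence is limited. The one-week reading is not a listed endpoint, its analysis is exploratory, and the primary VAS comfort and secondary OSDI analyses do not use it. The conclusion rests on assumed clinic hours between 09:00 and 18:00 and on no unseen instruction overriding Section 7.2; the Patient Instruction Guide is a separate document.

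**What to change.** 1. Reconcile the Visit 2 and 4 preparation rule and steps 2.9 and 4.9 with Appendix D, 2.3. Which rule should give way is for the sponsor and investigator; this review takes no view.
2. State whether the Visit 2 and 4 reading is meant to show the eye with product on it or the state of the tear film.
3. Record the clock time of the last instillation before LipiView, if the drop usage questions do not already capture it.
4. If same-day dosing is kept, declare it in steps 2.9 and 4.9 as a planned departure from Appendix D. Define the result in Sections 2.2 and 14.7 as an on-drop reading at the recorded elapsed time, not as one-week lipid layer status.
5. Reconcile the Visit 1 and 3 same-day wording with Appendix D as well, for subjects whose habitual drop is oil-based.

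The cost is protocol wording and possibly one extra eCRF field. The one-week lipid result will support a narrower claim. Elapsed time that goes unrecorded cannot be reliably recovered after the visits, so the change should precede the first Visit 2.
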